Occurrence of any of the below mentioned AESI should trigger a review by the SRC before proceeding with the dose escalation/s (Stage 1) or the next dose (Stage 2):

1. Fat atrophy that extends > 2 cm from an injection point or is > 10% of the treated area or is associated with tenderness lasting > 24 hours.
2. Pain limiting self-care activities of daily living (ADL) lasting more than 72 hours after active intervention (e.g. analgesic).
3. Skin atrophy that extends beyond area of any erythema or induration or is > 10% of the treated area or is associated with tenderness lasting > 24 hours.
4. Any skin hyper or hypopigmentation at the target area and/or the surrounding skin lasting for > 4 weeks.
* The color change reflecting from the bruising color is not included. The color changes due to deposition or loss of pigment in epidermal tissue is considered as hyper or hypopigmentation.
5. Any skin ulceration at the target area and/or the surrounding skin.

6. Any urticaria at the target area and/or the surrounding skin requiring oral treatment, lasting for > 72 hours.
7. Telangiectasia at the target area and/or the surrounding skin lasting for > 7 days.
8. Local numbness and/or paresthesia lasting for > 7 days.

Above mentioned AESIs are to be reported to the Sponsor within 24 hours upon notification by Investigator and/or delegates.

Study Stopping Criteria:

Administration of IP in a dose group may be paused, and additional subjects will not receive further treatments, until a consultation has taken place between the Investigator, the MM, and the Sponsor representative under the following circumstances:

- Any subject experiences an adverse event as Grade 3 (as defined in the National Cancer Institute-Common Terminology Criteria for Adverse Events [NCI-CTCAE] version 5.0) for cardiovascular, renal or hepatic event considered to be at least possible related to IP,
- Except for cardiovascular, renal, or hepatic events specified in Criterion #1, any participant experiences an AE as Grade 4 and considered to be at least possibly related to IP;
- Any subject experiences a serious adverse event (SAE) that is considered to be at least possibly related to IP;
- An AE or group of AEs that singularly or in aggregate suggests to the Investigator or Sponsor that the IP is poorly tolerated and further treatment per protocol (PP) may not be safe.

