 - a. For Group 1 (320 mg) in Stage 1, thigh subcutaneous fat thickness of at least 1.00 cm (10.0 mm) and up to 4.00 cm (40.0 mm) measured by ultrasound at Screening and Day 1.
 - b. For Group 2-4 (480 mg-800 mg) in Stage 1, abdominal subcutaneous fat thickness of at least 2.00 cm (20.0 mm) and up to 5.00 cm (50.0 mm) measured by ultrasound at Screening and Day 1.
 - c. For Stage 2, abdominal skinfold thickness of at least 3.00 cm (30.0 mm) and up to 8.00 cm (80.0 mm) by pinch method (measured by calibrated caliper) at Screening.
4. Subject has stable body weight (identified as ≤ 5% weight change per subject report) for at least 3 months before Screening and during the study.
5. Subject who has maintained a stable lifestyle (e.g. exercise, eating patterns, and smoking habit) per subject report for at least 3 months before Screening and during the study.
6. Voluntarily signs the Informed Consent Form (ICF) and, in the opinion of the Investigator or delegate, is physically and mentally capable of participating in the study, and willing to adhere to study procedures.

Exclusion Criteria:

A subject who meets **any** of the following exclusion criteria must be excluded from the study:

1. Female subject of childbearing potential who is not willing to commit to an acceptable contraceptive regimen with her partner from the time of Screening and throughout study participation until 90 days after the last IP dose, or who is currently pregnant or lactating. Male subject who is not willing to commit to an acceptable contraceptive method.
Note: Subjects who are not of childbearing potential are not required to use contraception. Females with no childbearing potential are defined as who have been surgically sterilized (hysterectomy or bilateral oophorectomy) or who are post-menopausal (defined as at least 50 years with ≥ 12 months of amenorrhea with a follicle stimulating hormone (FSH) > 40 IU/L).
2. Subject diagnosed with coagulation disorders or is receiving anticoagulant/antiplatelet therapy or medications or dietary supplements, which impede coagulation or platelet aggregation.
3. Subject has hemoglobin A1c (HbA1c) ≥ 9%, delayed wound healing, or any diabetic risks which, in the opinion of Investigator, is inappropriate to participate in the study.
4. Subject has a clinically significant cardiovascular disease and abnormal findings in electrocardiogram (ECG).

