5. Subject with active or prior history of malignancies within 5 years before Screening or being worked-up for a possible malignancy. Except adequately treated basal cell carcinoma of skin and in situ squamous cell carcinoma of skin would be eligible as per Investigator's discretion.
6. Subject with a history of human immunodeficiency virus (HIV)-1, infection or subjects with active HIV infection at Screening with positive HIV antigen/antibody (Ag/Ab) combo test.

7. Subject with a history of Trypanophobia, the extreme fear of medical procedures involving injections or needles, or who experience vasovagal syncope and faint or pass out at the sight of blood or a needle.
8. Subject has abnormal skin or local skin conditions at the treatment area, which in the opinion of Investigator, is inappropriate to participate in the study, including but not limited to any of the following:
 - a. Skin manifestations of a systemic disease,
 - b. Any abnormality of the skin or soft tissues of the area to be treated,
 - c. Grade III cellulite (Nürberger and Muller scale, [Nürberger F, 1978](#)) at the area to be treated,
 - d. Skin folding or fat folding on abdomen
 - e. Sensory loss or dysesthesia in the area to be treated,
 - f. Evidence of any cause of enlargement in the area to be treated other than localized abdominal or thigh subcutaneous fat,
 - g. Tattoos on the area to be treated.
9. Subject who has undergone the following procedures:
 - a. Previous surgery which caused scar tissues on the anticipated treatment area before Screening or during the study, except laparoscopic surgery and surgery which cause very small scar tissues would be eligible as per Investigator's discretion,
 - b. Liposuction to the region to be treated before Screening or during the study,
 - c. Esthetic procedure e.g. cryolipolysis, ultrasonic lipolysis, low level laser therapy (LLLT), lipolysis injection to the region to be treated within 12 months before Screening or during the study.
 - d. Using medication which is delivered via subcutaneous injection at the treatment area during the study period.
10. Subject is on prescription or OTC weight reduction medication or weight reduction programs within 3 months before Screening or during the study.

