- 4 Ultrasound – Thickness of fat will be obtained by ultrasonic measurements across target area. Abdominal or thigh ultrasound will be performed at Screening, Day 1, and Week 4. Abdominal or thigh ultrasound may be performed within 4 days before Day 1 and up to 4 days before/after Week 4 follow-up visit. Day 1 ultrasound can be exempted if the screening ultrasound is performed within 4 days prior to IP dose, and the screening ultrasound can be accepted as the Baseline value.
 - 5 A complete physical examination will include, at a minimum, assessments of the cardiovascular, respiratory, gastrointestinal, and neurological systems.
 - 6 On Day 1, injection site assessments will be performed pre-dose and at 1-hour post-dose.
 - 7 On Day 1, vital signs assessments to be performed pre-dose and at 1-hour post-dose. Vital sign assessments include temperature, pulse rate, blood pressure, and respiratory rate. At simultaneously scheduled assessments, vital signs will be collected prior to any blood draws.
 - 8 On Day 1, ECG assessments will be performed pre-dose only. ECG to be performed in supine position after at least 5 minutes rest. The following ECG parameters will be recorded: heart rate, RR interval, PR interval, QT interval, QTc interval, and QRS interval.
 - 9 Blood tests include biochemistry, hematology, and coagulation assessments. Biochemistry assessments include albumin, ALT, AST, ALP, triglyceride, total cholesterol, LDL-C, HDL-C, TBIL, GGT, urea, creatinine, eGFR, HbA1c, FBS, Sodium, Potassium, Bicarbonate, and Chloride. Hematological assessments include Hb, Hct, RBC count, mean corpuscular volume, Leukocyte/white blood cell (WBC) count, WBC differential, and platelet count. Coagulation assessments include aPTT, Prothrombin time, and INR.
 - 10 Urinary samples for dipstick will be collected. On Day 1, collection will be performed pre-dose only.
 - 11 Serum β -hCG test will be taken for WOCBP at Screening visit only. FSH test is required for females who are post-menopausal at the Screening visit. Urine β -hCG strip test will be taken WOCBP for other scheduled visits.
 - 12 Virology tests include HIV/HBV/HCV infection test. Active HIV infection is detected by detectable positive HIV Ag/Ab combo test; active HBV: HBsAg; active HCV: positive anti-HCV antibody.
 - 13 On Day 1, photography will be performed pre-dose and at 1 hour post-dose on Day 1. Other timepoints on Day 1 can be added to record the ISR at the discretion of the Investigator.

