9.2. Subject Exclusion Criteria

A subject who meets **any** of the following exclusion criteria must be excluded from the study:

1. Female subject of childbearing potential who is not willing to commit to an acceptable contraceptive regimen with her partner from the time of Screening and throughout study participation until 90 days after the last IP dose, or who is currently pregnant or lactating. Male subject who is not willing to commit to an acceptable contraceptive method. For details on contraception, refer [Section 9.3.2](#).

Note: Subjects who are not of childbearing potential are not required to use contraception. Females with no childbearing potential are defined as who have been surgically sterilized (hysterectomy or bilateral oophorectomy) or who are post-menopausal (defined as at least 50 years with ≥ 12 months of amenorrhea with a FSH > 40 IU/L).

2. Subject diagnosed with coagulation disorders or is receiving anticoagulant/antiplatelet therapy or medications or dietary supplements, which impede coagulation or platelet aggregation.
3. Subject has HbA1c \geq 9%, delayed wound healing, or any diabetic risks which in the opinion of Investigator is inappropriate to participate in the study.
4. Subject has a clinically significant cardiovascular disease and abnormal findings in ECG.
5. Subject with active or prior history of malignancies within 5 years before Screening or being worked-up for a possible malignancy. Except adequately treated basal cell carcinoma of skin and in situ squamous cell carcinoma of skin would be eligible as per Investigator's discretion.
6. Subject with a history of HIV-1 infection or subjects with active HIV infection at Screening with positive HIV Ag/Ab combo test.
7. Subject with a history of Trypanophobia, the extreme fear of medical procedures involving injections or needles, or who experience vasovagal syncope and faint or pass out at the sight of blood or a needle.
8. Subject has abnormal skin or local skin conditions at the treatment area, which in the opinion of Investigator is inappropriate to participate in the study, including but not limited to any of the following:
 - a. Skin manifestations of a systemic disease,
 - b. Any abnormality of the skin or soft tissues of the area to be treated,
 - c. Grade III cellulite (Nürnberger and Muller scale, [Nürnberger F, 1978](#)) at the area to be treated,
 - d. Skin folding and fat folding on abdomen
 - e. Sensory loss or dysesthesia in the area to be treated,

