14.1.7.5. Viral Serology

HIV Ag/Ab combo test, HBsAg, HBV surface and core antibody test, and HCV antibody testing will be performed at Screening.

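### Exclusion 4 requires both clinically significant cardiovascular disease and an abnormal ECG, so read literally it does not exclude a subject with such disease and a normal ECG

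*Protocol*

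**What the plan says.** The cardiovascular exclusion appears twice. The synopsis has "Subject has a clinically significant cardiovascular disease and abnormal findings in electrocardiogram (ECG" and Section 9.2 has "Subject has a clinically significant cardiovascular disease and abnormal findings in ECG". Both use *and*, and the phrase *clinically significant* is attached to the disease, not to the ECG findings.

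The stopping criteria (synopsis and Section 8.4) include a Grade 3 adverse event "for cardiovascular, renal or hepatic event considered to be at least possible related to IP". Related events in other organ systems trigger only at Grade 4. When a criterion is met, administration in the dose group may be paused until the investigator, medical monitor and sponsor representative have consulted.

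Table 10 (Section 14.2.1.2) defines the possibly related category so that it includes events with a reasonable time sequence that concurrent disease or other drugs could also explain.

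An ECG is done at Screening in both stages (Tables 4 and 5), and the investigator or designee reviews every tracing (Section 14.1.6). SAP Section 11.4 sorts ECG interpretations into normal, abnormal not clinically significant, and abnormal clinically significant.

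**The concern.** An exclusion criterion is applied as written, by different people at different sites in a multicenter trial. Here the written form asks for two findings together. Clinically significant cardiovascular disease can be present with a normal resting ECG, and on the literal text that combination passes.

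The protocol itself treats cardiovascular events as a special case by giving them a lower trigger grade. If a subject enters with known disease and then has a Grade 3 cardiovascular event, that disease is a competing explanation, yet the event can still be rated possibly related and so meet the trigger. Stage 1 has open-label groups of six with no control arm, and ECGs are part of its primary safety endpoint (Section 7.2.1.1). One event of unclear cause is hard to interpret in that setting, and Stage 1 safety data inform the Stage 2 dose. There is also the risk to the subject that the criterion presumably exists to avoid.

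**Working it through.** No arithmetic applies and the plan states no figure to reproduce. The check sets the texts side by side.

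**1. What exclusion 4 does under each reading.** The columns are the literal text, a bare change of *and* to *or*, and two separate conditions with the ECG one limited to clinically significant findings (CS = clinically significant, NCS = not clinically significant).

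| Cardiovascular disease (CS) | ECG | Literal text | Bare *or* | Separate, ECG limited to CS |
|---|---|---|---|---|
| Yes | Abnormal, CS | Excluded | Excluded | Excluded |
| Yes | Abnormal, NCS | Excluded | Excluded | Excluded |
| Yes | Normal | **Not excluded** | Excluded | Excluded |
| No | Abnormal, CS | **Not excluded** | Excluded | Excluded |
| No | Abnormal, NCS | Not excluded | **Excluded** | Not excluded |
| No | Normal | Not excluded | Not excluded | Not excluded |

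The third row is the main gap. The fifth row shows why a bare *or* is not a good repair: it would exclude any subject with a trivial ECG abnormality, although the SAP recognises abnormal findings that are not clinically significant.

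**2. Whether another criterion closes the gap.**
- Exclusion 2 removes subjects on anticoagulant or antiplatelet treatment. That covers some people with cardiovascular disease, not all.
- Inclusion 6 asks for the investigator's opinion that the subject is physically capable of taking part. The withdrawal criteria (Section 9.6) allow removal for a medical condition on the investigator's view of the subject's interest. Both are general judgements, not rules about cardiovascular disease.
- Exclusion 15, for the liver, has an open-ended limb covering any hepatic condition that would interfere with the assessments. Exclusion 4 has no such limb.

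The gap is therefore narrowed by judgement but not closed by rule.

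**3. Whether the subject's own disease can meet the stopping criterion.** The criterion needs a Grade 3 cardiovascular event that is at least possibly related. Table 10 does not bar that rating when concurrent disease is an alternative explanation. So the criterion can be met, although relatedness must first be judged and the result is a permitted pause.

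**4. Related wording.**
- Table 4, footnote 12 labels screening results "active HBV: HBsAg; active HCV: positive anti-HCV antibody". Table 5, footnote 11 lists the same hepatitis tests without calling the results active. Section 14.1.7.5 adds antibody tests: "HIV Ag/Ab combo test, HBsAg, HBV surface and core antibody test, and HCV antibody testing will be performed at Screening". The only virology result named in an exclusion is HIV (exclusion 6: "subjects with active HIV infection at Screening with positive HIV antigen/antibody (Ag/Ab) combo test"). Nothing states what a positive hepatitis result means for eligibility.
- Exclusion 8d reads "Skin folding or fat folding on abdomen" in the synopsis and "Skin folding and fat folding on abdomen" in Section 9.2.

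**The case against.** The strongest reply is that the drafters use *and* and *or* loosely, as item 8d shows, so the strict reading of exclusion 4 may be a drafting artefact that no investigator would apply. That is possible. But the conjunction is repeated in the operative section, and neighbouring criteria (2, 3, 6 and 15) use *or* where alternatives are meant. A site cannot tell which sense is intended, and two sites could apply it differently and both be compliant.

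Second, the stopping criterion is discretionary, and causality assessment must consider medical history and other risk factors. Pre-existing conditions that do not worsen are not adverse events (Section 14.2.1), and ECG, vital-sign and laboratory data are summarised as change from baseline. All of this stands. It limits the concern to new or worsening events and means that a trigger is possible, not automatic.

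Third, a reader might infer that subjects with hepatitis B or C are likewise eligible as written, because no exclusion names those results. The documents do not support that. Besides cirrhosis and liver tests above 3.0 × ULN, exclusion 15 covers any hepatic condition that would interfere with assessment of safety or efficacy, and an active hepatitis can fall under it. What is missing is only a statement of how positive serology is handled when liver tests are at or below that limit.

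Fourth, the 8d mismatch is clerical. Item 8 is a non-exhaustive list subject to the investigator's opinion, so its connective has little practical effect.

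**Conclusion.** The point holds for the cardiovascular exclusion. As written in both places, exclusion 4 does not exclude clinically significant cardiovascular disease with a normal ECG, and no other criterion reliably does so. This is out of step with the protocol's own decision to set a lower trigger grade for cardiovascular events.

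Its size cannot be given. The documents contain no prevalence of such disease in the target population and no event rate. A reader might try to turn the table of combinations, or one subject's share of a six-subject group, into a measure of risk; neither is one.

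The conclusion rests on reading *and* as a true conjunction. If the sponsor meant two separate exclusions, the defect is one of wording only, but the wording still has to change. The hepatitis serology and the 8d connective are minor clarifications.

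**What to change.** In the synopsis and Section 9.2, reword exclusion 4 as two separate conditions, each sufficient alone, with the ECG condition limited to clinically significant findings so that it matches the categories in SAP Section 11.4. If the sponsor intends both conditions to be required together, it should state this, give the reason, and reconcile it with Section 8.4. The choice of clinical rule is the sponsor's; the two sections should carry one unambiguous version.

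As minor clarifications, state how the Screening hepatitis B and C results bear on exclusion 15, or that they carry no eligibility consequence, and use the same connective in item 8d in both places.

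The change is a few words in two sections. The ECG and virology tests are already done at Screening, so no procedure is added. The downside is possibly a few more screen failures.

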4. LIST OF ABBREVIATIONS AND DEFINITIONS OF TERMS

The following abbreviations and specialist terms are used in this study protocol.

Table 2: Abbreviations and Specialist Terms

Abbreviation or Specialist Term	Explanation
ADL	Activities of daily living
AE	Adverse event
AESI	Adverse event of special interest
Ag/Ab	Antigen/antibody
ALT	Alanine aminotransferase
ALKP/ALP	Alkaline phosphatase
ASAPS	American Society for Aesthetic Plastic Surgery
AST	Aspartate aminotransferase
ATC	Anatomical therapeutic chemical
β-hCG	Beta human chorionic gonadotropin
BMI	Body mass index
CFR	Code of Federal Regulations
CI	Confidence interval
CSR	Clinical study report
CTCAE	Common Terminology Criteria for Adverse Events
ECG	Electrocardiogram
eGFR	Estimated glomerular filtration rate
EOS	End of study
EOT	End of treatment
ET	Early termination
FDA	Food and Drug Administration
FBS	Fasting blood sugar
FSH	Follicle stimulating hormone
GCP	Good Clinical Practice
GGT	Gamma-glutamyl transferase
GLP	Good Laboratory Practice
GMP	Good Manufacturing Practice
Hb	Hemoglobin
HbA1c	Hemoglobin A1c

Abbreviation or Specialist Term	Explanation
HBV	Hepatitis B Virus
HCV	Hepatitis C Virus
HDL	High-density lipoprotein
HED	Human equivalent dose
HIFU	High intensity focused ultrasound
HIV	Human immunodeficiency virus
IB	Investigator's Brochure
ICF	Informed Consent Form
ICH	International Conference for Harmonisation
IEC	Independent Ethics Committee
IP	Investigational product
IRB	Institutional Review Board
ISR	Injection site reaction
ITT	Intent-to-treat
IUD	Intrauterine device
LDL	Low-density lipoprotein
LLLT	Low level laser therapy
MedDRA®	Medical Dictionary for Regulatory Activities
MM	Medical monitor
NOAEL	No-observed-adverse-effect-level
OTC	Over-the-counter
PP	Per protocol
PT	Preferred term
RBC	Red blood cell
SAD	Single ascending dose
SAE	Serious adverse event
SAP	Statistical analysis plan
SD	Standard deviation
SOC	System organ class
SOP	Standard operating procedure
SRC	Safety Review Committee
TBIL	Total bilirubin

Abbreviation or Specialist Term	Explanation
TEAE	Treatment emergent adverse event
TGA	Therapeutic Goods Administration
ULN	Upper limit of normal
US	United States
VAS	Visual Analogue Scale
WBC	White blood cell
WHO	World Health Organization
WOCBP	Woman of childbearing potential

6. BACKGROUND AND INTRODUCTION

6.1. Introduction

6.1.1. Unmet Medical Need

The focus on body aesthetics and appearance continues to influence the treatment-seeking behavior of several people in the modern society. The most popular body contouring approaches used to improve the cosmesis of subcutaneous fat deposits are surgical and include liposuction, abdominoplasty, and thigh lifts, among other procedures. This increasing demand has led to the rapid growth and development of noninvasive, non-surgical treatment techniques. Although surgical techniques can result in the most pronounced outcomes in respect to improved body contouring results, they are also associated with inherent risk and complications such as pain, swelling, prolonged recovery, scarring, hematoma or infection, which make noninvasive procedures increasingly popular ([Adatto MA, 2014](#); [Kennedy J, 2015](#)).

The risks, financial costs and lengthy downtime associated with surgical procedures for fat reduction have led to the development of a number of noninvasive techniques ([Kennedy J, 2015](#)). In the recent years, noninvasive body contouring techniques have become one of the most widespread procedures and are growing fast in areas of esthetic medicine ([Nestor MS, 2013](#)). Noninvasive treatment approaches are painless, safe, and require little to no downtime ([Adatto MA, 2014](#)).

According to reported data by the American Society for Aesthetic Plastic Surgery (ASAPS) in 2013, the significant risk of invasive body contouring procedures has led to 521% growth of noninvasive techniques since 1997 ([Rotunda AM, 2006](#)). In addition, it has been estimated that noninvasive body contouring procedures are growing by 21% annually ([Atiyeh BS, 2008](#)). Even for shortening postoperative recovery, decreasing bruising and more skin tightening, surgical lipectomy techniques are combined with noninvasive methods ([Atiyeh BS, 2008](#)).

Commonly used treatment options for abdominal and thigh subcutaneous fat have been limited to invasive surgical or non-surgical procedures. Lipoplasty (including thigh liposuction) was the second most popular procedure performed by ASAPS members in 2019, with 270,670 procedures performed. Thigh lifts were performed at a rate of 9,815 in 2019 by ASAPS members ([ASAPS, 2019](#)). Unfortunately, surgical liposuction under general anesthesia carries significant potential risk and complications to a person seeking an aesthetic improvement; 2 independent surveys of board-certified aesthetic plastic surgeons in the United States (US) determined the mortality rate to be approximately 20 deaths per 100,000 procedures ([Grazer FM, 2000](#)). As for non-surgical procedures, there are now numerous options for fat reduction which utilize medical devices to deliver certain frequency of energy or cold temperature through the skin to ablate subcutaneous fat cells in the anterior abdomen, such as radiofrequency (RF), high intensity focused ultrasound (HIFU), Cryolipolysis or LLLT ([Friedmann DP, 2015](#)). In many cases (e.g., cryolipolysis, HIFU), these non-surgical procedures also cause inflammation which is related to the mechanism of removing the ablated fat cells from the treated area ([Jalilian HR, 2012](#)). This inflammatory process may result in pain, swelling and redness along with the increased recovery time for the process to complete and time to view aesthetic benefit. In addition, the cost of these devices as well as the disposables required must be taken into consideration for each treatment.

There is another non-surgical treatment for reducing subcutaneous fat which is known as mesotherapy or lipodissolve, a minimally invasive procedure. Mesotherapy involves a series of injections of medications that are purported to melt away localized fat deposits. Combinations of drugs such as phosphatidylcholine and deoxycholate (commonly called PC and DC, respectively), DC alone or combinations including other drugs or products such as vitamins, minerals, and herbal extracts may be used (Rotunda AM, 2006, Atiyeh BS, 2008). However, warning letters were issued by the Food and Drug Administration (FDA) to medical spas offering mesotherapy for unfounded claims of efficacy (Atiyeh BS, 2008, Duncan D, 2011). There were also numerous reports of significant AEs (e.g., skin necrosis, infections, etc.) due to unregulated mesotherapy (Atiyeh BS, 2008, Duncan D, 2011). This creates an unmet medical need to develop an injectable alternative with promising efficacy and an acceptable safety profile to fulfill the need of reducing abdominal and thigh subcutaneous fat.

